Effect of a Cold Water Immersion (CWI) on Pain in People with Gouty Arthritis: A Community Based Randomized Controlled Trial

Unique Protocol ID: N201912052

April 26, 2020

Effect of a Cold Water Immersion (CWI) on Pain in People with Gouty Arthritis: A Community Based Randomized Controlled Trial

1. Introduction

Gouty arthritis is a type of autoinflammatory arthritis (Rock et al., 2014) that generates higher pain (Carroll et al., 2018). Although the hospitalization rate in people with rheumatoid arthritis has declined, gout is growing (Fields, 2019). Gouty arthritis causes inflammation pain with only minimum movement in the joint. The inflammatory process causes central sensitization that can lead to chronic-long-term pain (Harth & Nielson, 2019). The pain among people with gouty arthritis is shown to negatively correlate with the physical function that encompasses reduced peak ankle joint angular mobility velocity, foot-specific disabilities, and impairment. It will probably represent the weakness of gait and experience disability (Carroll et al., 2018). People with gouty arthritis were found to have 1.18-times more likely to have a poor physical function (Burke et al., 2015). As such, we can conclude that gout arthritis diseases will lead to inferior extremity impairment, foot-specific disabilities, raises intolerance foot pain, physical inactivity, and joint mobility reduction.

Currently, intermittent drugs use for pain relief is suggested to contribute to the renal impairment side effect. Consequently, the renal impairment is attributed to the under-excretion of uric acid, kidney stones, and progress with many comorbidities (Fields, 2019; Padang, Muirden, Schumacher, Darmawan, & Nasution, 2006). Furthermore, terminal renal insufficiency has also long been implicated as a common cause of death in gout (Padang et al., 2006). However, we found that there is a limited study that investigated non-pharmacological intervention among people with gouty arthritis (Abhishek & Doherty, 2018).

The pain among people with gouty arthritis has also been shown to increase the degree of depression and psychological distress (Harth & Nielson, 2019). The prior studies conveyed the more pain will produce a huger degree of anxiety and depression (Fu et al., 2017; Hilderink, Burger, Deeg, Beekman, & Oude Voshaar, 2012; Lin, Zhang, & Ma, 2018). A significant relationship was also found between stress and the incidence of gouty arthritis in Southeast Celebes, Indonesia, in 2017 (Jaliana, Suhadi, La Ode, & Sety, 2018). Also, the high levels of pain, psychological distress, anxiety, and depression among people with gouty arthritis were found as the risk factor of poor Quality of Life (QOL) (Chandratre et al., 2018; Fu et al., 2017; Singh et al., 2017). Multiple studies reflect the impact of gout on life quality and its association with higher mortality (Chandratre, Mallen, Roddy, & Liddle, 2016; DiBonaventura, Andrews, Yadao, & Kahler, 2012; Fields, 2019). However, non-pharmacological therapy remains has been seldom studied among people with gouty arthritis on QOL, stress, anxiety, and depression. Therefore, non-pharmacologic treatment is vital in supporting people with gouty arthritis who are increased pain, reduced Quality of life, stress, anxiety, and depression.

A significant decrease of TNF- α level and considerable improvement of clinical severity of pain, duration of morning stiffness, and the degree of self-reported fatigue among people with Rheumatoid Arthritis (RA) were also founded in cryotherapy twice a day for ten days at -160 $^{\circ}$ C on the knee joint and 4 hours later on the joint of both hands (Jastrząbek, Straburzyńska-Lupa, Rutkowski, & Romanowski, 2013). Cold therapy (cryotherapy) application has been proven as useful adjuvant therapy on alleviating pain among people with gouty arthritis. A previous studies that applied the topical ice therapy on patients people with gouty arthritis who had experienced previous gouty flare attacks, showed a symptomatic improvement after 1 week of treatment (19 minutes on each treatment) compared to before topical ice therapy and control group (Schlesinger,

2006; Schlesinger et al., 2002). This cooling therapy reduces hyperemia and has also been presented to decrease experimental crystal-induced inflammation (Schlesinger, 2006). Since the application of cooling therapy is limited in short duration, Schlesinger (2006) suggested that the reaction of inflammatory arthritis among people with gouty arthritis should be assessed frequently in the future study. Moreover, the effects of topical ice therapy and cryotherapy have not been conducted in the community setting, an innovative and relevant cooling therapy with a multicenter-community setting to estimate its effect on people with gouty arthritis is strongly recommended.

Cold Water Immersion (CWI) is categorized as one of the Cryotherapies (Bleakley et al., 2012). CWI therapy has a twofold reduction of inflammation. Firstly, it attenuates metabolic processes in stressed tissues and slowing cytokine and myokine up-regulation that mediate inflammation. Second, CWI induces microvasculature vasoconstriction by perfusing stressed tissue; consequently, it reduces the circulatory exposure of tissue access to inflammatory cells (White & Caterini, 2017). CWI was defined as water immersion to a temperature of up to 15°C (Bleakley et al., 2012). A prior study has been proven that a short term effect of CWI therapy significantly reduced the level of pressure pain among 12 males (Klich, Krymski, Michalik, & Kawczyński, 2018). On the other hand, low temperature could induce gout crystal formation (Albar, 2007). As there was a controversial result of low temperature on joint crystal inflammation (Albar, 2007; Schlesinger, 2006), it was suggested to modify the CWI therapy on 20-30°C. Moreover, the CWI (20-30°C) therapy has not been done among people with gouty arthritis worldwide.

Meanwhile, the high prevalence of gouty arthritis has been presented in North Celebes, Indonesia (Health Research and Development Agency, 2013). Moreover, patients frequently presented too late for effective therapy; consequently, the chronic topical gout has contributed to the permanent deformities and impairments. When disability develops, and patients become dependent on their families. Data showed that more than 50% of patients had observed tophi for 7 to 9 years before presenting for treatment. It was due to the lack of information among people with gouty arthritis and primary healthcare professionals, and the lack of availability of urate-lowering drugs in community health centers (CHC) in Indonesia (Padang et al., 2006). These empirical issues indicate that the marked clinical and economic impact of gouty arthritis and the requirements of further research on successful gout management. Due to the previous studies limitation on cooling therapy, we aim to fill the gaps to investigate a unique analysis of the CWI (20-30°C) therapy effect on pain, joint mobility, stress, anxiety, depression, QOL (encompasses PCS and MCS), physical activity (MET-h/week) in the multicenter-community setting with randomized controlled trial study design.

2. Methods

2.1. Design

The randomized control trial study with two parallel-intervention-groups was employed to examine the effect of CWI (20-30^oC) therapy. All participants were randomly assigned to either CWI (20-30^oC) therapy intervention group or the control group. Block random sampling was then employed to generate the intervention and control group sequence. All participants were assessed on their pain as the primary outcome, joint mobility, stress, anxiety, depression, QOL including overall quality of life, physical component summary (PCS), and mental component summary (MCS), physical activity (metabolic equivalent of task–hour/week; MET-h/week) at three times points: before the intervention, 2nd and 4th-week of the intervention. Due to the nature of the intervention, it is only possible to blind the evaluator of the study. The CONSORT diagram of this

[figure not shown]
study is exhibited in Figure 1. The study protocol was reviewed and approved by the Institutional Review Board Ethics Committee of Taipei Medical University (N201912052), Taipei, Taiwan, and Universitas Kristen Satya Wacana, Salatiga, Indonesia (187/PE/KEPK.UKSW/2019), and conformed to the provisions of the *Declaration of Helsinki*. Written informed consent was obtained from each participant after they had received both verbal and written information about the research.

2.2. Setting and Participant

The sample calculation utilized G-Power 3.1 software with the alpha level (α) of 0.01, power (1- β) of 0.80 (Cohen, 1998), and the effect size is 0.9 (Klich et al., 2018), the total estimated sample size required 31 in each group. An estimated 20% dropout rate increases; the sample size is 36 for each group.

This research was conducted at North Celebes, Indonesia. Participants were recruited using the multi-stage sampling method. North Celebes Province was conveniently selected in the first stage sampling, which had the highest prevalence of gouty arthritis. North Celebes province was stratified it into 15 regions. In the second stage, two regions of fifteen regions were randomly selected, including urban and rural areas. Tomohon City is the one urban area that has been able to engage in this partnership. Seven Community Health Service (CHS) centers in Tomohon City have been randomly chosen in the final level. The inclusion criteria included (1) people with gouty arthritis in the knee or ankle or metatarsophalangeal or metacarpophalangeal or olecranon bursa or wrist, (2) participants were Indonesian nationals and aged ≥18 years, (3) they had visited a clinic of the Public CHS of Tomohon City, and (4) they had agreed to participate in the study. Participants, who self-reported the presence of other types of inflammatory arthritis, including RA

or spondyloarthritis, were excluded from the study. The data source of diagnoses was their medical records in the Public CHS of Tomohon City.

[figure not shown]

Figure 1. Flow of participants

2.3. Cold Water Immersion Intervention and Procedures

The participants maintained their daily activities during the intervention. When daily activity ended, the intervention was begun. CWI therapy immersed the whole part of the inflamed target joints in the water at 20-30°C for 20 minutes/day. The intervention was continued for four weeks. The researchers work together with the nurses of Community Health Services (CHS) to give the intervention. The nurses provide data that contains people who are diagnosed with gouty arthritis. Thereby, started with the participants' recruitment, intervention, and evaluation, the researchers collaborated with the CHS nurses to approach participants.

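### No record of immersion is named for either arm, yet missing data are handled per protocol, so lack of effect cannot be separated from non-adherence or control-arm uptake

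*Combined protocol and SAP*

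**What the plan says.** **Allocation and setting.** Section 2.1 states that "All participants were randomly assigned to either CWI (20-30^oC) therapy intervention group or the control group". The control condition is named but not described. The same section says that only the evaluator can be blinded and that participants receive oral and written information about the study. Section 2.2 recruits from one city: "Seven Community Health Service (CHS) centers in Tomohon City have been randomly chosen in the final level".

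**Intervention.** Section 2.3 sets immersion of the inflamed joint at 20-30°C for 20 minutes a day over four weeks, begun once the day's activities are over. Researchers and CHS nurses give it jointly, and the section adds that "started with the participants' recruitment, intervention, and evaluation, the researchers collaborated with the CHS nurses to approach participants". That sentence concerns contact with participants. It does not say that sessions are logged, or that each one is supervised.

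**Measurements.** Sections 2.4.1 to 2.4.6 cover blood pressure, BMI, a demographic and lifestyle questionnaire (with gout drugs, alcohol and smoking), food frequency, VAS pain, goniometry, DASS-21, SF-36 and MET-h/week. No item concerns immersion or other cold use.

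**Analysis.** Section 2.5 compares the arms by GEE at a significance level of 0.05 and gives per-protocol as the way missing data are handled. It does not say what following the protocol means.

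**Sample size.** Section 2.2 uses "the alpha level (α) of 0.01, power (1- β) of 0.80", and "the effect size is 0.9". It makes no allowance for participants who do not immerse as assigned.

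**The concern.** Deviation is plausible in both directions. A control participant who knows what the study is about could copy the treatment with a basin of water. A CWI participant has about 28 daily sessions to complete (4 weeks x 7 days), and some may miss sessions or stop.

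Two things are at stake. First, if pain differs little between arms, the trial would have no data to show whether immersion does not help or whether the two arms did much the same thing. Second, a per-protocol analysis needs a rule for who followed the protocol and data to apply it. With neither, two analysts could form different sets from the same trial. Removing people for what they did after randomisation also leaves groups that are no longer comparable by design.

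**Working it through.** **Step 1. Set the sections side by side.** Section 2.3 defines an exposure by minutes, temperature and days. Section 2.4 names no variable for any of these in either arm. Section 2.5 names an analysis set that depends on them. The per-protocol set therefore cannot be derived from the variables the plan describes.

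**Step 2. Reproduce the plan's sample size.** Section 2.2 says "The sample calculation utilized G-Power 3.1 software" but gives neither the test nor the sidedness. A two-sided two-sample t-test with equal groups gives the plan's figure.

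- Inputs: d = 0.9, alpha = 0.01, power 0.80.
- Noncentrality at n = 31 per group: d x sqrt(n/2) = 0.9 x sqrt(15.5) = 3.543, on 2 x 31 - 2 = 60 degrees of freedom.
- Critical value: 2.660. Power: 0.808.
- At n = 30, power is 0.791, so 31 is the smallest n that reaches 0.80.

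This matches "the total estimated sample size required 31 in each group". The calculation assumes the full effect of 0.9 between the arms, that is, everyone immerses in one arm and no one in the other.

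**Step 3. Illustrate the dilution.** The documents give no deviation rates, so those below are assumptions. Let s be the share of the CWI arm that does not immerse and c the share of controls that does. If everyone is analysed in the assigned arm, the SD is unchanged and the effect is 0.9 in those who immerse and zero otherwise, then

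expected d = 0.9 x (1 - s - c).

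Power is shown at both alphas, because section 2.2 sizes the trial at 0.01 and section 2.5 tests at 0.05.

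| s | c | Expected d | Power, n = 31, alpha 0.01 | Power, n = 31, alpha 0.05 |
|---|---|---|---|---|
| 0 | 0 | 0.90 | 0.808 | 0.937 |
| 10% | 10% | 0.9 x 0.8 = 0.72 | 0.572 | 0.796 |
| 20% | 10% | 0.9 x 0.7 = 0.63 | 0.435 | 0.685 |
| 20% | 20% | 0.9 x 0.6 = 0.54 | 0.306 | 0.553 |

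If all 36 per group were analysed, the second row would be 0.658 and 0.854, and the third 0.513 and 0.751.

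**Step 4. Limit of the illustration.** The formula describes an analysis by assigned arm. Section 2.5 states a per-protocol method instead. If that means excluding deviators, the problem is selection: those who stop, or those controls who start, may differ in pain from those who do not. The direction and size of that bias cannot be worked out from the documents.

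**The case against.** Four objections carry weight.

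- **Staff would see it.** A reader might infer that switching would be invisible. The documents do not support that for the CWI arm: researchers and nurses give the intervention and may notice when someone stops. What the plan lacks is a stated record. For controls it describes no means of noticing at all.
- **The trial would still answer a question.** A reader might infer that a null result could not be interpreted. That goes too far: a comparison by assigned arm would still estimate the effect of being offered CWI. What is lost is the ability to tell an ineffective treatment from one that was not taken up, or was taken up in both arms.
- **The list may not be complete.** Section 2.4 does not claim to be exhaustive, the lifestyle questionnaire is described by its main items, and the flow diagram (Figure 1) is not visible. This is fair, so the point is confined to the readable text. It does not supply the missing definition of adherence in section 2.5.
- **The rates are invented.** They are assumptions, and no document shows that controls copy the treatment. At the analysis alpha of 0.05, deviation of 10% in each arm still leaves power of about 0.80. The table shows what moderate deviation could do, not what will happen.

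**Conclusion.** The point holds in this form: the readable plan names no record of immersion in either arm, and it relies on a per-protocol method without defining adherence. Non-adherence and control-arm uptake could therefore not be separated from lack of effect, and the analysis set could not be formed reproducibly. Excluding deviators would put the randomised comparison at risk of bias in an unknown direction.

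The loss of power depends on deviation rates that the documents do not give. At 31 per group it runs from modest (0.937 to 0.796, for 10% in each arm at alpha 0.05) to serious (0.808 to 0.435, for 20% and 10% at alpha 0.01). These figures assume analysis as assigned, an unchanged SD and no effect without immersion. The conflict between sections 2.3, 2.4 and 2.5 rests on none of these assumptions. The change should be made: it is cheap, and exposure that is not recorded during the four weeks cannot be reliably recovered later.

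**What to change.** - **Section 2.3:** enter each CWI session on a card with date, minutes, water temperature and joint.
- **Section 2.4:** at the existing week 2 and week 4 assessments, ask both arms about all self-care of the painful joint. Record days of water immersion, with approximate temperature, separately from days of ice use. A single question on cold water or ice would not match the 20-30°C exposure under study.
- **Section 2.5:** replace the per-protocol method with a primary GEE analysis of all randomised participants in their assigned group, using every available visit. Report exposure by arm. Keep any per-protocol analysis as supportive, with adherence defined before the data are seen.
- **Optional:** an analysis that uses randomisation as an instrument for immersion. Label it exploratory, because it assumes that assignment affects pain only through immersion. In an unblinded trial with self-rated pain, expectation could act directly. It would also be imprecise at this sample size.

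**Cost.** A card, one short question at two planned visits and revised analysis text. The question may prompt some controls to try immersion; asking about self-care in general limits this. Much of the document is written in the past tense. If the sessions are already over, only the section 2.5 change remains possible, and the absence of exposure data should be reported as a limitation.

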2.4. Measurements

2.4.1. Participants characteristic

Four qualified professional nurses collected all the data. Blood pressure and BMI were examined in a standardized medical examination. Demographic data were collected by using a self-designed questionnaire. The questionnaire included the demographic characteristics of the participant, including age, gender, marital status, educational level, income, occupation, family gout history, gouty arthritis drug consumption, alcohol consumption, and smoking status (Tsai et al., 2007). The translated food frequency questionnaire was employed with Cronbach's alpha as 0.95 (Nilawati, Nugraheni, & Frieda, 2005).

2.4.2. Pain

The Visual Analog Scale (VAS) instrument has 10 centimeters length. The standard scale anchored by "no pain" marked as a score of 0 and the "worst imaginable pain" marked as a score of 10 cm (Huskisson et al., 1974; Scott & Huskisson, 1976). The higher score identifies greater pain intensity. The reliability test showed that VAS was good (r = 0.94, p = 0.001) (Ferraz et al., 1990). The reliability test of the VAS instrument has been done in Indonesia with the Cronbach's alpha as 0.89 (Suwendar et al., 2017).

2.4.3. Joint mobility

The range of knee joint motion was calculated using an International Standard Orthopedic Measurement (ISOM) goniometric. Its method using the Sagittal Frontal Transverse Rotation (SFTR) system to an accuracy of 1^o (Dorwart, Hansell, & Schumacher, 1974). Goniometry provides an objective assessment tool to measure the range of motion (Rose & Norton, 1987). The validity and reliability of Goniometry are 0.98 and 0.97, respectively (Rose & Norton, 1987). The validity score of the Indonesian

version is 0.97, and the Cronbach alpha as 0.51 (Hafiyah, 2013).

2.4.4. Stress, anxiety, depression

The Depression Anxiety Stress Scale (DASS-21) questionnaire is used to measure the negative states of three mental health conditions: depression, anxiety, and stress using a self-report 4-point Likert scale. Data was collected by reflecting thoughts, feelings, and behavior (Oei, Sawang, Goh, & Mukhtar, 2013). The result will be defined by the total scores of responses from the 7-item subscale of this questionnaire. The Cronbach's alphas of Indonesian translated is 0.72 to 0.87 (Susilowati, Isahak, & Harncharoen, 2016).

2.4.5. Quality of Life (QOL)

The 36 Health Survey (SF-36) questionnaire was employed to estimate QOL. It included Physical Component Summary (PCS), Mental Component Summary (MCS). Total QOL range from 0 to 100 (Rias et al., 2020). The Indonesia version of the SF-36 questionnaire has tested the reliability with the Cronbach's alphas 0.7 (Salim, Yamin, Alwi, & Setiati, 2015)

2.4.6. Physical activity (MET-h/week)

The physical activity level was investigated as metabolic equivalent of task (MET)-hr/week by calculating the arbitrary units of summing the products of the separate components using the formula: (MET)-hr/week score =(MET level x hours x times/week) (Rias et al., 2020) We then estimated physical activity levels based on the exercise type (that is divided into the following categories: mild (e.g., yoga, bowling, or floor-sweeping), moderate (e.g., gym, baseball, or badminton), and strenuous exercise (e.g., hiking, soccer, or running)), duration in hours and exercise frequency

they presented during a typical week. We multiplied the amount of mild, moderate, and strenuous exercise hours and duration by 3, 5, and 9. By summing the exercise pattern of the separate things, we measured total weekly physical activity in arbitrary units (Rias et al., 2020).

